**LIST OF ABBREVIATIONS**

ADC	Apparent Diffusion Coefficient
AE	Adverse Event
ALT	Alanine Aminotransferase
ALC	Absolute Lymphocyte Count
ASCO	American Society of Clinical Oncology
ASL	Arterial Spin Labeled
AST	Aspartate Aminotransferase
BUN	Blood Urea Nitrogen
CBC	Complete Blood Count
CEST	Chemical Exchange Saturation Transfer
CMP	Comprehensive Metabolic Panel
CR	Complete Response
CT	Computed Tomography
CTCAE	Common Terminology Criteria for Adverse Events
DCE	Dynamic Contrast Enhanced
DLT	Dose Limiting Toxicity
DOT	Disease Oriented Team
DSC	Dynamic Susceptibility Contrast
DSMB	Data and Safety Monitoring Board
DWI	Diffusion Weighted Imaging
ECOG	Eastern Cooperative Oncology Group
FDA	Food and Drug Administration
GCP	Good Clinical Practice
H&P	History & Physical Exam
HRPP	Human Research Protections Program
IDE	Investigational Device Exemption
IHC	Immunohistochemistry
IND	Investigational New Drug
IV (or iv)	Intravenously
MGMT	O6-methylguanine-DNA methyltransferase
MRI	Magnetic Resonance Imaging
MTD	Maximum Tolerated Dose
NCI	National Cancer Institute
NSF	Nephrogenic Systemic Fibrosis
ORR	Overall Response Rate
OS	Overall Survival
PBMCs	Peripheral Blood Mononuclear Cells
pCR	Pathologic Complete Response
PD	Progressive Disease
PET	Positron Emission Tomography
PFS	Progression Free Survival

p.o.	peros/by mouth/orally
PR	Partial Response
RANO	Response Assessment in Neuro-Oncology
RCB	Residual Cancer Burden
RCC	Renal Cell Carcinoma
RECIST	Response Evaluation Criteria in Solid Tumors
SAE	Serious Adverse Event
SCCC	Simmons Comprehensive Cancer Center
SD	Stable Disease
SGOT	Serum Glutamic Oxaloacetic Transaminase
SPGT	Serum Glutamic Pyruvic Transaminase
WBC	White Blood Cells

## STUDY SCHEMA

MRI including ASL will be performed before, during and after the treatment, in a total of 6 MRI sessions, or when progression is clinically indicated. The baseline MRI will be performed up to 7 days before the treatment initiation. The first two follow-up MRIs will be performed on day  $7\pm 2$  and day  $14\pm 2$  after treatment initiation, with the option of participating at both time points. The last three time points (\*) will be performed along with the patient's clinical imaging. Thereafter, patients will be followed through standard clinical examinations for the next 3 years or until demise, whichever occurs first.

## STUDY SUMMARY

Title	A Prospective Study to Evaluate Quantitative Non-Contrast Perfusion using Arterial Spin Labeled MR Imaging for Assessment of Therapy Response in Metastatic Renal Cell Carcinoma
Short Title	Quantitative MRI for therapy response assessment in metastatic RCC
Protocol Number	STU 032018-078
Phase	N/A
Methodology	Prospective study to evaluate quantitative MRI metrics for the assessment of treatment response
Study Duration	48 months
Study Center(s)	Single-center
Objectives	To prospectively determine whether ASL-measured perfusion can identify treatment response earlier than the currently used RECIST criteria.
Number of Subjects	90 (40 subjects with RCC and 50 healthy volunteers)
Diagnosis and Main Inclusion Criteria	Diagnosis: Locally advanced or metastatic renal cell carcinoma Main Inclusion Criteria: Patients with histologically proven clear cell RCC, scheduled to undergo anti-angiogenic treatment or immunotherapy (IO) who are 18 years of age and older and have no contraindication to MRI.
Study Product(s), Dose, Route, Regimen	N/A
Duration of administration	N/A
Reference therapy	N/A
Statistical Methodology	Primary end points for this study will include the absolute days of time to disease progression, progression free survival (PFS) and overall survival (OS) as well as disease status (progression versus not) at 7 months post treatment initiation. Progression will be determined according to the clinical RECIST criteria. One-sample correlation test will be used to determine the correlation between change in ASL measured tumor perfusion during and immediately after treatment and time to progression, and the correlation between change in ASL measured tumor perfusion and the corresponding tumor size change. The correlations will be measured and compared using Pearson's correlation coefficient along with 95% confidence interval. PFS and OS will be correlated with baseline perfusion and post-treatment changes at T1, T2 and T3 compared to baseline using univariable and multivariable Cox regression models. Univariable and multivariable logistic regression models will be used to predict responders from non-responders (progression versus not at 7 months) with ASL measurements at baseline and at earlier time points (T1 and T2) alone, and in combination with other MR imaging metrics.

## 1.0 BACKGROUND AND RATIONALE

### 1.1 Disease Background

The incidence of kidney cancer has steadily increased over the past three to four decades and is among the 10 most frequently diagnosed cancers in the US.

Approximately 63,990 new cases of kidney cancer are estimated in 2017 and the prognosis has been historically poor (1). The current 5-year survival rates are estimated at 74% overall, decreasing to 53% among patients with locally advanced diseases (2).

The most common form of kidney cancer, renal cell carcinoma (RCC), occurs in 90% of all kidney cancers. Among patients with localized RCC who are treated with nephrectomy, approximately one quarter have relapses in distant sites. Among patients with metastatic RCC, the 5-year survival rates are approximately 8%. With better understanding of the pathogenesis of the most common type of RCC, clear-cell renal cell carcinoma (ccRCC), newer treatment options with new agents are being developed to increase survival rates (3).

[figure not shown]
The high cost and potential risks associated with human trials for the newly developed experimental therapies have emphasized the need for sensitive monitoring of tumor response. Imaging approaches can play an important role in the evaluation and selection of potential new therapies with non-invasive longitudinal monitoring of treatment response (4). Currently, the radiological assessment of treatment outcomes predominantly relies on morphological (i.e. size) changes using the Response Evaluation Criteria in Solid Tumors (RECIST) and other similar scores (5). This is a major limiting factor as the effects of many therapeutic agents at the microscopic level precede the eventual changes in tumor size. One such tumor property that has gained increased attention is angiogenesis (6), which has been shown to support tumor proliferation and infiltration. Increasing numbers of clinical trials have begun targeting tumor vascular supplies by directly inhibiting angiogenesis (e.g. antiangiogenic therapy) (7). *Such clinical trials and the eventual clinical use of these therapies would be greatly assisted by the availability of robust imaging indicators of angiogenesis (i.e. tissue perfusion).*

Positron Emission Tomography (PET) using  $^{15}\text{O}$ -labeled water ( $^{15}\text{O}$ -PET) is considered the gold standard for non-invasive measurement of tissue perfusion (8). However, the use of  $^{15}\text{O}$ -PET requires a cyclotron in close proximity to PET to produce short lived  $^{15}\text{O}$ -water (half life 2.4 min), limiting its applicability in clinical settings (9). Alternative imaging techniques include ultrasound using microbubbles, perfusion computed tomography (CT) using iodinated contrast agent and perfusion MRI using gadolinium based contrast agents (10). All of these techniques require exogenous agents, restricting their use in longitudinal monitoring of treatment response.

#### **Arterial Spin Labeled (ASL) – MRI:**

ASL-MRI has recently emerged as a quantitative imaging (QI) method to measure perfusion (or capillary blood flow) without the administration of exogenous contrast agents (11). ASL magnetically “labels” the highly permeable water in the blood as a tracer and measures their accumulation in the tissue of interest, without injecting any exogenous contrast. Various versions of ASL have been validated in animals using microspheres (12), and in humans using  $^{15}\text{O}$ -PET in the brain (13,14). ASL also has a number of advantages compared to dynamic contrast enhanced (DCE) and dynamic susceptibility contrast (DSC) based MR perfusion measurements. Specifically, ASL does not require exogenous agent alleviating the concerns of gadolinium accumulation (15,16) or nephrogenic systemic fibrosis (NSF) in patients with impaired renal function (17) and, unlike DCE/DSC, the contribution of vascular permeability to ASL measured perfusion is

negligible (18) enabling absolute perfusion quantification in physiological units (ml/100g/min).

ASL-MRI consists of three distinct steps to achieve absolute quantification of tissue perfusion (Fig. 1). First, the acquisition of two images – a control image, where the blood and the static tissue is at its full magnetization and a label image, where only the inflowing blood is selectively inverted while the static tissue is maintained at its full magnetization. Second, the image reconstruction including the subtraction of labeled images from the control images to generate a perfusion-weighted image (PWI). Third, the perfusion quantification by modeling of PWI using a proton-density image and acquisition parameters to account for tissue characteristics to generate a quantitative perfusion map in physiological units of ml/100g/min. Both control and label images are acquired without administering any exogenous contrast agent, but using MR principles. The control image is acquired similar to other standard MR images. The label image is also acquired similar to other standard MR images, except that the inflowing blood such as the arterial blood in the abdominal aorta is selectively inverted using radiofrequency (RF) pulses and gradients (Fig. 2, yellow solid box). During the acquisition of control and label images, the subjects do not experience anything additional except the standard MR gradient noise and RF heating (that stays within the FDA guidelines) similar to any other standard MR examination.

## 1.2 Study Agent(s) Background and Associated Known Toxicities

This study will not investigate or focus on the role of any agents.

Gadolinium-based contrast agent for MRI such as Gadavist (generic Gadobutrol) or Dotarem (generic Gadoterate acid), are FDA-approved contrast agents for the diagnostic study and will be used in this study.

## 1.3 Other Agents

Not applicable (N/A).

Figure 2. The yellow box shows the ASL labeling plane, across the abdominal aorta. Using MR principles including selective RF pulses and gradients, the inflowing blood in the abdominal aorta at this labeling plane is selectively inverted with ASL.

#### **1.4 Rationale**

Recent discoveries in the biology of RCC have led to the development of targeted agents (e.g. vascular endothelial growth factor (VEGF)). Five of the FDA approved drugs for the treatment of metastatic RCC (bevacizumab, sunitinib, sorafenib, pazopanib, and axitinib) target either VEGF or its receptor. Clinically, these patients are followed every 2-3 months after therapy initiation and treatment response is primarily evaluated using size changes (i.e. Response Evaluation Criteria In Solid Tumors (RECIST)) (5). However, rapid changes in ASL measured perfusion may predict tumor targeting better than size change, allowing better patient management. This study is targeted to demonstrate this capability in metastatic RCC patients.

#### **1.5 Correlative Studies**

Standard clinical history including clinical histopathology will be collected and correlated.

### **2.0 STUDY OBJECTIVES**

#### **2.1 Primary Objectives**

- 2.1.1 To determine whether ASL-measured perfusion can identify treatment response (time to progression) earlier than the currently used RECIST criteria in patients undergoing anti-angiogenic treatment.

#### **2.2 Secondary Objectives**

- 2.2.1 To determine the correlation between ASL-measured baseline perfusion and the treatment response (PFS, OS).
- 2.2.2 To determine the correlation between post-treatment changes in ASL-measured perfusion at T1, T2 and T3 compared to baseline and the treatment response (PFS, OS).
- 2.2.3. To predict responders from non-responders (progression versus not at 7 months) with measurements at baseline and at earlier time points (T1 and T2) using:
  - a. ASL-measured perfusion alone
  - b. ASL-measured perfusion in combination with other MR imaging metrics such as diffusion weighted imaging (DWI) derived apparent diffusion coefficient (ADC), and chemical exchange saturation transfer (CEST) measured CEST effect.

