#### **2.4 Endpoints**

Primary end points for this study will include the absolute days of progression free survival (PFS) and overall survival (OS). Additionally disease status (progression versus not) at 7 months and survival (dead or alive) at 24 months post-treatment initiation will also be documented. Progression will be determined based on the clinically accepted RECIST criteria.

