#### 5.4 Time and Events Table

##### RCC Subjects

	Pre-study	Week 0 (T0) before initiation of anti-angiogenic therapy	Day 7±2 (T1)	Day 14±2 (T2)	T3	T4	T5	Follow-up (As indicated by clinical protocol)
Assessment	X							
Informed Consent	X							
History and PE	X							
Tumor Measurements	X							
MRI*		X	X	X	X	X	X	X

\*Clinically, metastatic RCC patients are imaged every 2-3 months after the initiation of anti-angiogenic therapy, since morphological (i.e. size) changes are not anticipated earlier. However, our preliminary experience has shown functional changes including perfusion as early as 2-weeks after the initiation of the treatment (19). T0, T1, and T2 sessions will be performed for this proposal, while T3, T4, and T5 will be performed along with the clinical imaging sessions. The research MR imaging may take approximately an additional 15 minutes per each imaging session, when done in conjunction with the clinical imaging. The T0, T1, and T2 research MR imaging sessions will be performed additionally for the purpose of this study, with each taking approximately one hour.

The ASL portion of the study does not require contrast. Clinically, the subjects will also receive gadolinium based contrast injection for the MRI study to measure the blood flow to the tumors. This is done at the clinical imaging time points of T3, T4, and T5. Similar to this, the contrast agent will also be administered during the research portion of the study at T0, T1 and T2 time points, to compare the blood flow measured with ASL-MRI.

MRI including ASL will be performed before, during and after the treatment, in a total of 6 MRI sessions until 7 months after the first session, or when progression is clinically indicated. Thereafter, patients will be followed through standard clinical examinations for the next 3 years or until demise, whichever occurs first.

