#### 6.1.5 Progression-Free Survival

Progression-free survival (PFS) is defined as the duration of time from start of treatment to time of progression.

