**10.3 Data Analyses Plans**

The perfusion difference images and the absolute quantified images will be converted to DICOM and transferred to a DICOM database (e.g. iPACS, OsiriX). A semi-automated segmentation algorithm and region of interest (ROI) based measures will be performed to extract perfusion measures. Percentage changes in perfusion within each ROI will be calculated at each follow-up MRI compared to the baseline image. The semi-automated tumor ROIs will be compared to expert segmentation by [name] in all cases, who will also supervise the trainee (to be recruited) in the analysis. Additionally, morphological changes will also be calculated according to RECIST and 10% reduction in the sum of the largest diameters (20).

Among patients with disease progression, one-sample correlation test will be used to determine the correlation between change in ASL measured tumor perfusion during and immediately after treatment and time to progression, and the correlation between change in ASL measured tumor perfusion during and immediately after treatment and the corresponding tumor size change. The correlations will be measured and compared using Pearson's correlation coefficient along with 95% confidence interval. PFS and OS will be correlated with baseline perfusion and post-treatment changes at T1 and T2

compared to baseline using univariable and multivariable Cox regression models. We used PFS at 7 months as a cutoff point to divide patients into “responders” versus “non-responders” in this study. Univariable and multivariable logistic regression models will be used to predict responders from non-responders with ASL measurements at baseline and at earlier time points (T1 and T2) alone, and in combination with other MR imaging metrics. The statistical analysis will also be performed separately for male and female subjects to evaluate sex as a biological variable.

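### T3 perfusion change is in Objective 2.2.2 and the Study Summary but not in Section 10.3; if it is kept, the Cox model for PFS needs a landmark, because T3 is probably the first RECIST scan

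*Combined protocol and SAP*

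**What the plan says.** Three places describe the same analysis, and they differ on T3.

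- Section 2.2, Objective 2.2.2, concerns "post-treatment changes in ASL-measured perfusion at T1, T2 and T3 compared to baseline" and their correlation with PFS and OS. It names no model.
- The Study Summary (Statistical Methodology) names the model: "post-treatment changes at T1, T2 and T3 compared to baseline using univariable and multivariable Cox regression models".
- Section 10.3 states: "PFS and OS will be correlated with baseline perfusion and post-treatment changes at T1 and T2", again by Cox regression. T3 is not listed.

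The timing comes from three other places.

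- Section 6.1.5: "Progression-free survival (PFS) is defined as the duration of time from start of treatment to time of progression".
- Section 5.4, RCC table and footnote: "T3, T4, and T5 will be performed along with the clinical imaging sessions", and "metastatic RCC patients are imaged every 2-3 months after the initiation of anti-angiogenic therapy". No day is given for T3.
- Section 2.4: "Progression will be determined based on the clinically accepted RECIST criteria".

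No section gives a landmark, a time-dependent covariate, or a rule for patients who progress or die at or before T3.

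**The concern.** A Cox model with a fixed covariate and a clock that starts at treatment start treats the covariate as known on day 0. The T3 change is known only some 2-3 months later, probably at the visit where the first RECIST progressions are recorded. For a patient who progresses by then, the model relates the event to a perfusion value taken on the same day. If the progression was found clinically before T3, there may be no value at all, and the patient drops out of the model.

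Perfusion measured in a tumor that is already progressing can be associated with PFS without having any value for prediction. In a study whose hypothesis is that perfusion falls before size changes, such a result could be read as support that it does not provide.

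**Working it through.** **The plan's own figure.** The only power figure is for the primary correlation (Section 10.2: r = 0.75, about 20 progressors, two-sided 0.05, more than 95%). By Fisher's z, power = Φ(atanh(0.75) × √(20 − 3) − 1.96) = Φ(0.973 × 4.123 − 1.96) = Φ(2.05) = 98.0%. The figure is reproduced. It does not bear on the Cox models, for which the documents give no power, event or effect figure.

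**Inputs.** From Section 10.2: 40 patients, 50% progressing by 7 months, hence about 20 progressions. From Section 5.4: clinical imaging every 2-3 months. Assumed: T3 is the first clinical follow-up scan, and PFS is exponential.

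**Progressions by T3.** The fraction progressed by month m is 1 − 0.5^(m/7).

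| T3 at | Fraction | Of 40 | Share of the 20 | Still at risk | Progressions left to month 7 |
|---|---|---|---|---|---|
| 2 months | 18.0% | 7.2 | 36% | 32.8 | 12.8 |
| 2.5 months | 21.9% | 8.8 | 44% | 31.2 | 11.2 |
| 3 months | 25.7% | 10.3 | 51% | 29.7 | 9.7 |

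The same formula gives 0.9 of 40 by day 7 (T1) and 1.8 of 40 by day 14 (T2), so the problem is essentially one of T3.

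**Effect on the test for PFS.** Simulation with 40 patients and 1,500 trials per setting. Later scans are every 2.5 months, follow-up is 36 months, and every patient has a T3 value. The T3 change carries no information on later progression and is shifted only in patients who have progressed by T3. Cox regression uses Efron ties. The two values in each cell are for T3 at 2 and 3 months.

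| Shift (assumed) | Rejects at nominal 5%, clock from treatment start | Median HR per SD | Rejects with landmark at T3 |
|---|---|---|---|
| 0 | 5.6%, 4.7% | 1.00, 1.00 | 4.9%, 5.0% |
| 0.5 SD | 7.5%, 11.0% | 1.09, 1.13 | 4.8%, 4.3% |
| 1.0 SD | 20.8%, 31.7% | 1.20, 1.27 | 4.1%, 4.5% |
| 1.5 SD | 36.7%, 54.1% | 1.30, 1.40 | 4.6%, 4.0% |

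The plan does not state how ties are handled. With Breslow ties the test is conservative here (2.6% at no shift), and the three shifts give 5-6%, 14-22% and 26-44%. The pattern is the same.

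**Precision under the landmark.** The hazard ratio per SD detectable with 80% power and D events is exp((1.96 + 0.842)/√D). D = 20 gives 1.87, D = 12.8 gives 2.19, and D = 9.7 gives 2.46.

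**The case against.** The strongest reply is that Section 10.3 is the analysis plan, and it limits these models to T1 and T2. If it governs, the timing problem does not arise. That stands as far as it goes: a reader might infer that the trial has settled on a T3 Cox model, and the documents do not support this. But the objective and the Summary both keep T3, so some text has to change whichever governs.

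Four further limits stand.

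- A reader might extend the same-day argument to OS. Death is not read on the T3 scan. For OS the issue is only that a patient must live to T3 to have the covariate. The documents give no mortality figure from which to size this.
- A reader might infer that the error rate is inflated whatever the data look like. It is not. With no shift it stays at about 5%, and the documents give no figure for the shift.
- T3 as the first clinical scan is the natural reading of Section 5.4, but it is an inference. The week-3 label for T3 belongs to the healthy-volunteer table.
- A reader might infer that the early-detection claim falls with this analysis. That claim is the primary objective, tested by correlation among progressors, and the responder prediction in 2.2.3 is limited to baseline, T1 and T2. Objective 2.2.2 is secondary.

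**Conclusion.** The point holds in a limited form. The documents contradict each other on whether T3 enters the PFS and OS models. If it does, with PFS timed from treatment start and no further rule, 18-26% of patients (7-10 of 40) would have progressed on or before the day the covariate is measured. This rests on exponential PFS, the plan's 50% at 7 months, and T3 at 2-3 months.

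The harm to the PFS test depends on how far perfusion differs in patients already progressing: rejection in about 7-11%, 21-32% and 37-54% of trials at shifts of 0.5, 1.0 and 1.5 SD, and about 5% at none. A shift of some size is plausible, since the study's premise is that perfusion tracks response, but its size is unknown. Patients with no T3 value raise a separate question of selection, which the simulation does not cover. For OS there is only the milder condition of surviving to T3.

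**What to change.** Make the Study Summary, Objective 2.2.2 and Section 10.3 agree, in one of two ways.

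1. **Drop T3** from 2.2.2 and the Summary, leaving T1 and T2 as in Section 10.3.
2. **Keep T3** in all three places, and add to Section 10.3 a landmark rule that differs by endpoint.
   - PFS: start the clock at the T3 scan, in patients who are progression-free after that scan's RECIST read.
   - OS: start the clock at T3, in all patients alive at T3, including those who have progressed. To require freedom from progression here would wrongly drop living patients who are still at risk of death.
   - Any multivariable model that contains T3 takes the same landmark. Report the numbers at risk, the remaining events, and how many patients had no T3 value and why.

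An alternative to the landmark is to enter T3 change as a time-dependent covariate that acts only on later intervals.

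The first option costs wording and the T3 question itself. The second costs wording and precision. The PFS landmark keeps about 30-33 of 40 patients and about 10-13 of the 20 progressions expected by 7 months, so the detectable hazard ratio per SD rises from about 1.87 to about 2.2-2.5. It also answers a narrower question, about PFS after T3 in patients who reach T3 without progression. Models with T1 and T2 alone and the primary correlation analysis are unaffected.
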